**Table 5-13 Clinically notable criteria for selected Other Lab parameters**

Laboratory parameter	US or Other unit		SI unit	
	Lower bound	Upper bound	Lower bound	Upper bound

Notable value			
Dipstick proteinuria		$\geq 3^+$	$\geq 3^+$
FSH (male only)		$> 5$ (mIU/mL)	$> 5$ (U/L)
Troponin T		$\geq 14.0$ (ng/L)	$\geq 0.014$ (ug/L)
NTproBNP		$>125$ pg/mL	$> 14.75$ pmol/L
Dipstick Hematuria		$\geq 3^+$ on	$\geq 3^+$
Combined rules			
Urine protein-creatinine ratio		Dipstick proteinuria $\geq 3^+$ OR PCR $\geq 1$ g/g (or $\geq 113$ mg/mmol equivalent as converted by the measuring laboratory)	Dipstick proteinuria $\geq 3^+$ OR PCR $\geq 1$ g/g (or $\geq 113$ mg/mmol equivalent as converted by the measuring laboratory)
Notable relative change from baseline			
FSH (male only)		double from baseline and value $> 5$ mIU/mL	double from baseline and value $> 5$ (U/L)

**Table 5-14 Clinically notable criteria for Echocardiogram with GLS**

Parameter	Lower bound	Upper bound
Notable value		
Left Ventricular Ejection Fraction (LVEF)	$< -50\%$	

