Testicular atrophy	
Recommendation: If FSH level doubles from baseline and absolute value is above 5 IU/L then consult endocrinologist. Use clinical judgment for continuation of study drug; discuss with participant.

Neurologic Findings	
Neurologic Findings suggestive of peripheral neuropathy	
Recommendation: Consider withholding study drug under the following conditions:
 
 • Any clinically significant neurologic finding on the comprehensive neurologic exam with or without a positive response on neurology questionnaire. The following should be actioned: 
 • Perform Compound Motor Action Potential (CMAP)/ Sensory Nerve Action Potential (SNAP) 
Follow-up as per Investigators judgement
 
 • In case of inconclusive CMAP or SNAP results, Investigator may use clinical judgement regarding discontinuation or withholding study drug 
Mandatory: Discontinue study drug immediately and permanently under the following conditions:
 
 • Any clinically significant abnormality in the comprehensive neurology exam and CMAP or SNAP. Continue to follow patient (to resolution). Refer to Section 8.4.4
Ophthalmological Findings	-
Retinal Atrophy	
Recommendation: Any new retinal findings from baseline which in the opinion of the Investigator is related to the study drug, discontinue the study drug permanently. Manage as per standard of care.

Refer to [Appendix 1 \(Table 16-1 and Table 16-2\)](#) for guidance on hepatic events and [Appendix 2 \(Table 16-3 and Table 16-4\)](#) for guidance on renal events.

This guidance does not provide an exhaustive list of AEs and Investigators should use their clinical judgement when assessing dose interruption for those AEs not mentioned in the table.

Participants whose study treatment is temporarily interrupted or permanently discontinued due to an AE or abnormal laboratory value must be followed until resolution or stabilization of the event, whichever comes first, including all study assessments appropriate to monitor the event as described in this section. In the event study treatment has been temporarily interrupted (> 7 days) due to an AE or laboratory abnormality not listed in [Table 6-3](#), study treatment may be re-challenged to an every other week dosing after discussing with the Novartis.

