##### Summary tables

Descriptive statistics will be summarized for the following parameters by visit:

- Left ventricular ejection fraction (LVEF)
- Left Ventricular Global Longitudinal Strain (LVGLS)

The number and percentage of participants with clinically notable values at any post baseline visits will be summarized by period, parameters. The clinically notable are defined in [Appendix 5.5](#).

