##### Listings

---

Echocardiogram data will be listed for the participants with clinically notable values.

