**Table 5-12 Clinically notable criteria for selected chemistry tests**

Laboratory parameter	US or Other unit		SI unit	
	Lower bound	Upper bound	Lower bound	Upper bound
Notable value				
Sodium	120 (mmol/L)	160 (mmol/L)	120 (mmol/L)	160 (mmol/L)
Potassium	3 (mmol/L)	6 (mmol/L)	3 (mmol/L)	6 (mmol/L)
Magnesium	1 (mg/dL)	6.1(mg/dL)	0.4 (mmol/L)	2.5 (mmol/L)
Albumin	25 (g/L)		25 (g/L)	
Gamma-glutamyl-transferase (GGT)		3 X ULN		3 X ULN
estimated Glomerular filtration rate (eGFR)	<=30 (mL/min)		<=30 (mL/min)	
Lipase		1.5 x ULN		1.5 x ULN
Amylase		1.5 x ULN		1.5 x ULN
Notable relative change from baseline				
Creatinine*		>50%		>50%
* Baseline Creatinine is calculated as the average of screening and baseline (if either one is missing, the non-missing one will be used as baseline, if multiple screening assessments is available, average screening assessments first and then average with baseline)				

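### SAP Table 5-14 gives no criterion for GLS or for a fall in LVEF, so the echo notable-value count and listing planned in SAP 2.7.4.1 cannot be completed

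*SAP*

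**What the plan says.** SAP 2.7.4.1 (Echocardiogram with GLS) plans by-visit descriptive statistics for two parameters, LVEF and left ventricular GLS, using central readings. The next sentence reads: "The number and percentage of participants with clinically notable values at any post baseline visits will be summarized by period, parameters". The definitions are said to be in Appendix 5.5. The listing is restricted in the same way: "Echocardiogram data will be listed for the participants with clinically notable values".

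The only echocardiogram table in Appendix 5.5 is Table 5-14, "Clinically notable criteria for Echocardiogram with GLS". As printed it has one row, for LVEF, under the heading for notable values. The row has a lower bound and no upper bound. There is no GLS row and no change criterion.

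Protocol 8.4.2 names three echo findings as clinically relevant: LVEF below 50%, an LVEF reduction of at least 10% units, and a GLS change from baseline of at least 15% units. Protocol Table 6-3 repeats all three. Protocol 12.5.2 asks for counts of clinically significant abnormalities on cardiac assessments and includes echo with GLS among them. SAP section 4, the place for changes to protocol-specified analyses, holds only a back-reference.

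**The concern.** The SAP commits to an output by parameter and supplies a rule for only one of the two parameters. A programmer who follows it cannot derive the GLS count. For LVEF the count can be derived, but it omits a kind of decline that the protocol calls clinically relevant. Because the listing depends on the same flag, the affected participants also drop out of the listing.

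Cardiovascular effects are a listed potential risk in protocol Table 4-2, and safety is a primary objective. The planned echo flag is the direct route from a central reading to a participant-level statement in the report. The sponsor team was unblinded on 02-Nov-2022 and an interim analysis was done in April 2023, so a GLS cut-off picked during programming would be post hoc. Using the protocol's own thresholds avoids most of that difficulty.

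**Working it through.** The documents give no figure to reproduce. The check sets the protocol's thresholds against the SAP's criteria.

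| Finding called clinically relevant (protocol 8.4.2 and Table 6-3) | Type | Criterion in SAP Table 5-14 |
|---|---|---|
| LVEF below 50% | absolute value | yes, if the printed bound is meant as 50% |
| LVEF reduction of at least 10% units | change from baseline | none |
| GLS change of at least 15% units | change from baseline | none |

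Coverage is at most 1 of 3 overall, 0 of 2 for change from baseline, and 0 of 1 for GLS.

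**Which LVEF falls escape.** Let b be baseline LVEF and d the fall, both in percentage units, and assume the SAP bound is meant as below 50%. A fall meets the protocol's reduction threshold when d ≥ 10. It escapes the SAP flag when b − d ≥ 50. Both hold when 10 ≤ d ≤ b − 50, which has solutions for every b ≥ 60. For b under 60, a fall of 10 or more ends below 50 and is flagged. If the bound was meant as 50% or below, the escaping range is 10 ≤ d < b − 50, which has solutions for b above 60.

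Example with assumed values: LVEF goes from 65% to 53%. The fall is 65 − 53 = 12 units, so the protocol threshold is met. Since 53 is not below 50, the participant is neither counted nor listed.

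**Which GLS changes escape.** All of them, because there is no criterion to apply.

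**Is the protocol's GLS threshold ready to program?** Not quite. Read as absolute, it needs a change of 15 units. Read as relative, it needs 0.15 × g, where g is the size of the baseline value. The two agree only if 0.15 × g = 15, that is g = 100. For any smaller g the relative reading flags smaller changes. The wording also gives no direction.

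**How other tables in Appendix 5.5 treat change.** Tables 5-12 and 5-13 carry a block headed "Notable relative change from baseline". The FSH row in Table 5-13 ("double from baseline and value" above a limit) follows the protocol's rule in Table 6-3 ("If FSH level doubles from baseline and absolute value is above 5 IU/L"). So the SAP does in places carry a protocol change threshold into its notable criteria. That heading would not suit echo, because the protocol states the LVEF threshold in units.

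**The printed bound.** The LVEF bound appears as < -50%. Taken literally, no LVEF value could meet it. It is not a change criterion either, since it stands under the notable-value heading. It may be an artefact of text extraction, and nothing above relies on it.

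**The case against.** The strongest reply is that the SAP never undertakes to mirror the protocol's action levels. Its blood pressure criteria are >180 and >105 mmHg, against ≥160 and ≥100 in protocol Table 6-3. Its QTcF criteria are >450 msec or a 20% change from the previous visit, against >500 msec or >60 msec from baseline in protocol 6.5.2.1. Protocol 12.5.2 does not tie clinically significant abnormalities to the thresholds in 8.4.2, and protocol section 12 leaves detail to the SAP. This stands, and it makes the LVEF-change gap the softer of the two. It does not answer the GLS gap: in the blood pressure and QTcF examples a different criterion exists, while for GLS there is none.

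Layout and title are weak evidence. Table 5-9 puts changes inline, Table 5-10 uses change from the previous visit, and Tables 5-11 and 5-15 have no separate change block. Echocardiogram with GLS is also simply the name of the procedure. The missing block and the title therefore do not show an oversight. The point rests on the by-parameter count in 2.7.4.1.

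There are real backstops. By-visit statistics include the minimum and maximum by default (SAP 2.1). Protocol 8.4.2 has the central reader alert sites when the LVEF and GLS thresholds are met, and asks for clinically relevant abnormalities to be recorded as adverse events. The SAP summarises those events by organ class and term, by dose interruption or discontinuation, and by special-interest risk. They remain partial: the alert depends on site recording, group statistics do not identify individuals, and the echo section, unlike the ECG section, does not name change from baseline.

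A reader might go further in two ways that the documents do not support. One is to infer that cardiac findings will go unreported; the backstops contradict that, and no echo results are given. The other is to attach a probability of a missed case from the incidence rates in protocol Table 12-1. Those are hypothetical adverse event rates, and nothing links them to echo abnormalities that escape a flag.

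**Conclusion.** The point holds as an internal gap in the SAP. The planned GLS notable-value count has no criterion. The LVEF count and the listing omit falls of at least 10% units that end at or above 50%, which the protocol calls clinically relevant. The GLS part is firm; the LVEF part is a mismatch with the protocol that should be closed or explained.

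The impact is small. Treatment has stopped permanently, only Cohort 1 was enrolled, the report is abbreviated and descriptive, and no test or dose decision uses the flag. The number of participants affected cannot be estimated from the documents.

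The conclusion assumes that Table 5-14 has no rows beyond those printed. No gap or redaction is visible, but the source file should confirm it. It also assumes that the parameters in the count sentence are the two named just before it, which is the natural reading.

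**What to change.** For reporting flags only, reconcile SAP Table 5-14 with protocol 8.4.2 and Table 6-3:

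1. Add a block headed Notable change from baseline (not relative change) with the protocol's LVEF-reduction and GLS-change thresholds.
2. First state whether the GLS threshold of 15% units is absolute or relative, and in which direction. The central reader's alerts used this threshold, so its alert specification may already settle the reading. Record the choice and its date, since the team is unblinded.
3. If either threshold is dropped on purpose, say so with the reason in SAP section 4. If GLS is dropped, limit the notable-value count and the table title to LVEF.
4. Check the rows of Table 5-14 and the printed < -50% bound against the source file.

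The cost is two table rows and one clarification, or a sentence in section 4 with a changed title and count. No new assessments are needed; the protocol ended the echo requirement with the 06-Dec-2022 notification, and the SAP already plans to use the central readings. The documents do not say how complete those readings are. No treatment rule is changed.

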**Table 5-15 Clinically notable liver function test values**

Criterion

ALT > 3 x the upper limit of normal range (ULN)
ALT > 5 x ULN
ALT > 8 x ULN
ALT > 10 x ULN
ALT > 20 x ULN
ALT or AST > 3 x ULN
ALT or AST > 5 x ULN
ALT or AST > 8 x ULN
ALT or AST > 10 x ULN
ALT or AST > 20 x ULN
Total bilirubin (BILI) > 1 x ULN
Total bilirubin (BILI) > 1.5 x ULN
Total bilirubin (BILI) > 2 x ULN
ALP > 1.5 x ULN
ALP > 2 x ULN
ALP > 3 x ULN
ALP > 5 x ULN
ALT or AST > 3 x ULN and total bilirubin > 1.5 x ULN
ALT or AST > 3 x ULN and total bilirubin > 2 x ULN
ALT or AST > 5 x ULN and total bilirubin > 2 x ULN
ALT or AST > 8 x ULN and total bilirubin > 2 x ULN
ALT or AST > 10 x ULN and total bilirubin > 2 x ULN
ALT or AST > 20 x ULN and total bilirubin > 2 x ULN
ALP > 3 x ULN and total bilirubin > 2 x ULN
ALP > 5 x ULN and total bilirubin > 2 x ULN
ALT or AST > 3 x ULN and Total Bilirubin > 2 x ULN and ALP < 2 x ULN (Hy's law)

ALT = alanine aminotransferase, AST = aspartate aminotransferase, ALP = alkaline phosphatase

When a criterion contains multiple laboratory parameters, the criterion will only be considered to have been met when all conditions occur within a 3-day window. A case where all criteria are met at a post-baseline time point will be considered as newly occurring if the criteria are not met at baseline and will be considered as worsening if the criteria are met at baseline and at least one component is worsening from baseline irrespective of whether the other(s) are better. Rule of exclusion criteria of analysis sets.

## 5.6 Rule of exclusion criteria of analysis sets

**Table 5-16 Subject Classification**

Analysis Set	PD ID that cause participants to be excluded	Non-PD criteria that cause participants to be excluded
All analysis sets	NA	Not having informed consent
RAS/FAS/SAF/	NA	Not randomized

Analysis Set	PD ID that cause participants to be excluded	Non-PD criteria that cause participants to be excluded
FAS/SAF/	NA	No double-blind study drug taken

